15.3 Effect of BMS-986231 on furosemide concentration

Furosemide urinary and plasma concentrations and the ratio of urinary sodium to urinary furosemide will be calculated at each time point over 4-hour urine/plasma collection after a bolus injection of 40 mg furosemide while receiving BMS-986231 or placebo

Descriptive statistics (n, mean, SD, %CV, median, min, and max) will be used to summarize the absolute difference and the percent change from placebo of furosemide urine concentration, furosemide plasma concentration and the ratio of urinary sodium to urinary furosemide at 8 h by treatment.

Paired profiles of furosemide urine concentration, furosemide plasma concentration and the ratio of urinary sodium to urinary furosemide (4 h after furosemide dosing) will be provided for a visual representation of the data.

[REDACTED]

[REDACTED]

[REDACTED]

[REDACTED]

[REDACTED]

[REDACTED]

[REDACTED]

[REDACTED]

16.0 Pharmacokinetic Analyses

The PK summaries described in this section will be created using the Randomized analysis set.

16.1.1 Plasma Concentrations

Descriptive statistics (n, mean, SD, CV%, geometric mean, median, min, and max) will be used to summarize the plasma concentrations of Furosemide, BMS-986231 (and its metabolites) at each scheduled time point (see table in Appendix 3).

Plasma concentrations below the limit of quantification (BLQ) will be set to missing in the computation of mean concentration values. No descriptive statistics will be provided if more than half of the subjects have values BLQ.

All individual subject plasma concentration data will be listed.

16.1.2 Urine Concentrations

Urine recovery of Furosemide, BMS-986231 (and its metabolites) will be calculated per interval and cumulative. Parameters will be calculated as follows for 4-10 h for furosemide and for 0-10 h for BMS-986231 and metabolites:

Parameter	Description	SAS Programming Notes
Ae(0-T)	
Cumulative amount of drug excreted unchanged into urine to time t (last scheduled sample).
 
The amounts recovered in urine over a collection interval are calculated by multiplying the urine concentrations for each analyte by the total volume/weight of the sample collected during that interval.
 
The sum of the amount recovered for all intervals is calculated to obtain the total amount recovered in urine, obtained by adding the amounts excreted over each collection interval.
	Summation i = 1 to n of (Concentration (ng/mL) t_{i-1} - t_i) * volume(mL) t_{i-1} - t_i

Parameter	Description	SAS Programming Notes
Fe	
Fraction (represented in %) of the administered dose excreted unchanged into urine.
 
The sum of the percentage of dose for each analyte for all intervals will be calculated to obtain the total percentage urinary recovery.
	$(Ae(0-T)/Dose)*100$

All individual subject urine parameters (interval times, concentration, volume, amount excreted in interval) data will be listed.

Otherwise urine parameters will be summarized as described above.

Safety Analyses

The safety summaries described in this section will be created using the Safety set.

16.2 Safety Variables

The following safety variables will be included:

- Adverse Events
- Clinical Laboratory Evaluations
- Vital Signs
- Electrocardiograms

16.2.1 Adverse Events

An AE is defined as any new untoward medical occurrence or worsening of a preexisting medical condition in a clinical investigation participant that does not necessarily have a causal relationship with treatment. Treatment-emergent adverse events (TEAEs) are those which occur after the first dose of study drug. All TEAE summaries will be presented alphabetically by system organ class, with preferred terms sorted in decreasing order of frequency within each system organ class based on MedDRA dictionary.

For treatment period assignment, the following rules will be applied:

- TEAEs occurring following dosing in period 1 but before dosing in period 2 will be attributed to the drug administered in period 1.
- TEAEs occurring following dosing in period 2 will be attributed to the drug administered in period 2.

If the time is missing for an AE on a dosing day, then the AE will be attributed to the treatment period of the treatment given on that day.

The following missing data will be imputed (for calculations only) as defined:

- Missing AE start and / or end times for the calculation of onset and duration will be assumed to be at 00:01 for a start time and 23:59 for end times
- Missing AE severity or relationship will be left as missing
- Missing AE start times for the determination of treatment emergence will be assumed to occur after treatment unless partial date documents the AE as happening prior to treatment
- Missing AE start times for the determination of treatment assignment will be assumed to occur after treatment on the recorded date one minute after dosing
- Missing AE start date will be assumed to be after treatment for the determination of TEAE but will not be attributed to a specific treatment

A summary of the number and percentage of subjects reporting AEs, TEAEs by severity, serious AEs (SAEs), and who discontinue study drug due to an AE will be presented by treatment and overall.

A summary of the number and percentage of subjects reporting each TEAE will be presented by treatment and overall. Counting will be done by subject only, not by event; subjects will only be counted once within each body system or preferred term.

A summary of the number and percentage of subjects reporting each TEAE will be presented by relationship to BMS-986231 (as recorded on the CRF) and by treatment and overall. Subjects with multiple events will be counted under the category of their most-related event within each system organ class or preferred term.

A summary of the number and percentage of subjects reporting each TEAE will be presented by relationship to Furosemide (as recorded on the CRF) and by treatment and overall. Subjects with multiple events will be counted under the category of their most-related event within each system organ class or preferred term.

A summary of the number and percentage of subjects reporting each TEAE will be presented by severity (as recorded on CRF) and by treatment and overall. Subjects with multiple events will be counted under the category of their most severe event within each system organ class or preferred term.

All AEs (including non-treatment-emergent events) recorded on the eCRF will be listed by subject.

A separate listing of AEs leading to study drug discontinuation will be provided by subject.

16.2.2 Deaths and Serious Adverse Events

A listing of deaths and other SAEs will be provided by subject.

16.2.3 Laboratory Data

Clinical laboratory data will be presented using Système International (SI) units from the study data tabulation model (SDTM) Controlled Terminology.

A descriptive statistics summary of continuous laboratory results for chemistry and hematology and derived changes from baseline will be provided by scheduled time point.

All laboratory data will be listed by subject, including laboratory variables not listed in the protocol.

A separate listing of out-of-range values will also be provided. Normal ranges will be used directly from the clinical laboratory and will be included in the listings for reference.

Results from pregnancy tests will be listed.

16.2.4 Vital Signs

A descriptive statistics summary of vital signs and derived changes from baseline will be provided by treatment and scheduled time point.

All vital signs data will be listed by subject. A separate listing of hypotension will be provided.

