[REDACTED]				Washout between periods should be at least 7 days and no more than 4 weeks.
[REDACTED]	■		■	[REDACTED]
[REDACTED]	■		■	[REDACTED]

^a If end of infusion occurs prior to 8 hours after start of infusion (H8), the end of infusion should be considered early discontinuation. In case of an early discontinuation, the timing for the assessments will be adapted accordingly, ie, H8 will be immediately after end of infusion, H9 will be 1 hour after end of infusion, H10 will be 2 hours after end of infusion, H11 will be 3 hours after end of infusion, and H11.5 will be 3.5 hours after end of infusion, as applicable.

STUDY ACKNOWLEDGMENT/DISCLOSURE

I understand that this protocol contains information that is confidential and proprietary to Bristol-Myers Squibb Company (BMS). Any supplemental information that may be added to this document is also confidential and proprietary to BMS and must be kept in confidence in the same manner as the contents of this protocol.

I have read the original protocol and agree that it contains all necessary details for carrying out the study as described. I will conduct this protocol as outlined therein and will make a reasonable effort to complete the study within the time designated.

I will provide copies of the protocol and access to all information furnished by BMS to study personnel under my supervision. I will discuss this material with them to ensure that they are fully informed about the investigational product and the study.

I will provide protocol information to my Institutional Review Board(s) [IRB(s)] or Independent Ethics Committee(s) [IEC(s)]. I understand that original protocol/revised protocols must be reviewed by the Institutional Review Board or Independent Ethics Committee overseeing the conduct of the study and approved or given favorable opinion by all necessary Health Authorities before implementation unless to eliminate an immediate hazard to subjects.

I agree that the contents of the protocol may not be disclosed to any other person or entity or used for any other purpose without the prior written consent of BMS. The foregoing shall not apply to disclosure required by governmental regulations or laws; however, I will give prompt notice to BMS of any such disclosure.

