The Bioanalytical Sciences section or its designate may be unblinded to the randomized treatment assignments, in order to minimize unnecessary assays of samples from subjects during the placebo treatment period. Likewise, the Metabolism and Pharmacokinetics section or its designate may be unblinded, if metabolite profiling work is conducted.

In certain circumstances, a pharmacokineticist or designate(s) in Clinical Pharmacology and Pharmacometrics, biostatistician(s) and programmer(s) at BMS, or designee, may be unblinded in order to prepare preliminary summaries of PK and safety data, as needed. These summaries will not reveal individual subjects' treatment sequence assignments.

6.4 *Dosage Modification*

BMS-986231 or placebo

The administration of the study drugs will be done through an infusion pump connected to a single peripheral IV line. After priming the infusion set tubing and connecting the lines to the IV catheter, the pump should be set to deliver the rates of infusion indicated on the infusion bag label.

The pump infusion volume display should be re-set to 0 after priming the infusion line and just prior to the start of the infusion, and the total volume infused at the conclusion of the infusion after 8 hours, or at the time of any early discontinuation, should be recorded in the clinic source documents.

[figure not shown]
At any time during the administration of study drug, the study drug infusion must be discontinued if an AE or any other safety issue suggests it is not in the patient's best interest to continue to receive study drug.

The investigator has the option to adjust the study drug dosage level downward by 50%, interrupt or discontinue the study drug infusion in patients that develop hypotension, or if the patient experiences symptomatic hypotension that is not easily tolerated, as follows (and shown in [Figure 2](#)):

- **Study drug reduction:** Study drug is decreased by 50% if SBP decreases to levels <90 mmHg but \geq 80 mmHg. The dose cannot be subsequently increased.
- **Study drug interruption:** Study drug is interrupted for 1 hour if SBP <80 mmHg or symptoms of low blood pressure occur. If the SBP is \geq 105 mmHg after one hour interruption, the study drug could be resumed at 50 % of the dose.
- **Study drug discontinuation:** Study drug will be permanently discontinued if SBP remains < 105 mmHg after 1 hour interruption or if SBP decreases to levels <80 mmHg or symptoms of low blood pressure occur.

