All participants who discontinue study treatment should comply with protocol-specified follow-up procedures as outlined in the Schedule of Activities, Section 1.3. The only exception to this requirement is when a participant withdraws consent for all study procedures including post-treatment study follow-up or loses the ability to consent freely (ie, is imprisoned or involuntarily incarcerated for the treatment of either a psychiatric or physical illness).

If study treatment is discontinued prior to the participant's completion of the study, the reason for the discontinuation must be documented in the participant's medical records and entered on the appropriate CRF page.

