8.1.2 Imputation

Unless otherwise noted, data will not be imputed.

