Appendix 2: Schedule of Activities from Protocol

Table 1: Screening Procedural Outline (CV013-034)

Table 2: On Treatment Procedural Outline (CV013-034)

Procedure	Treatment Period			Notes
	Period 1 Day 1	Washout (7-28 days)	Period 2 Day 1	
Washout between periods should be at least 7 days and no more than 4 weeks.				
Safety Assessments				
Weight	X		X	Weight within 15 minutes prior to and within 15 minutes after the end of the infusion in each treatment period with bio-impedance scale. Weight should be measured after the void.
Targeted physical examination	X		X	To be done at H0 (before start of infusion). Based on subject's report since the last visit. Includes temperature, signs and symptoms of congestion. If the screening physical examination is performed within 3 days prior to first dosing then a single physical exam may count as both the screening and at H0 (before start of infusion) evaluation.
Vital Signs (Blood pressure and heart rate)	X		X	Prior to infusion, and 30 minutes for first hour then every 1 hour until discontinuation of infusion, then at H9, H10 and H11.5 (3.5 hour after end of infusion) in each treatment period.
Peripheral Oxygen Saturation	X		X	Prior to the start of infusion and immediately prior to the end of the infusion in each treatment period, measured with a pulse oximeter device.
12-lead ECG	X		X	Prior to the infusion and after end of infusion (both with 15 minutes window) in each treatment period. Triplicate ECGs will be recorded.
Telemetry	X		X	From start of infusion to 3 hours after end of infusion in each treatment period.
Adverse Events Assessment	X		X	Nonserious AEs will be collected from the start of the study drug infusion until 24 hours after end of infusion in each treatment period of dosing. Serious adverse events must be collected from the date of Informed consent and will be assessed up to 30 days after end of infusion of the last period.
			■	
			■	
Follow-up call/assessment	X		X	To be done at Day 2 of each period. Will inquire about general status and occurrence of any AEs.

Table 2:
On Treatment Procedural Outline (CV013-034)

Procedure	Treatment Period		Notes
	Period 1 Day 1	Washout (7-28 days)	Period 2 Day 1
Laboratory Tests			Washout between periods should be at least 7 days and no more than 4 weeks.

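### After an early stop, the by-time vital-sign table has no readings up to H7 for patients stopped for low blood pressure and then mixes re-timed with nominal readings from H8, so it is a poor guide to the on-infusion SBP fall

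*SAP*

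**What the plan says.** The planned summary is in SAP 16.2.4: "A descriptive statistics summary of vital signs and derived changes from baseline will be provided by treatment and scheduled time point". The schedule behind it, in the Vital Signs row of SAP Appendix 2, is half-hourly for the first hour and then "every 1 hour until discontinuation of infusion, then at H9, H10 and H11.5 (3.5 hour after end of infusion) in each treatment period".

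Footnote a to Table 2 in Protocol 1.3 treats any end of infusion before 8 hours as an early discontinuation and moves the later time points: "H8 will be immediately after end of infusion, H9 will be 1 hour after end of infusion", with H10 at 2 hours, and "H11.5 will be 3.5 hours after end of infusion, as applicable". Patients who stop stay on the schedule (Protocol 7.1): "All participants who discontinue study treatment should comply with protocol-specified follow-up procedures as outlined in the Schedule of Activities". The SAP's copy of the schedule does not carry this footnote, although SAP 3.0 says the SAP is to be read with the protocol.

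Low pressure is itself a reason to stop. One trigger in Protocol 6.4 is: "Study drug will be permanently discontinued if SBP remains < 105 mmHg after 1 hour interruption". Meeting the reduction or interruption criteria again after one down-titration is another.

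On missing values, SAP 8.1.2 says: "Unless otherwise noted, data will not be imputed". SAP 8.1.5 lists unscheduled readings but keeps them out of the descriptive statistics unless they serve as baseline. Hypotension during infusion is a named safety endpoint (SAP 5.2.2), yet its only dedicated output is a listing (SAP 16.2.4 and Appendix 4, Listing 16.2.10.2).

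**The concern.** The variable being averaged decides who is in the average. On BMS-986231 the mean at, say, H6 comes from patients whose pressure allowed the infusion to continue, whereas the placebo mean would be expected to come from nearly everyone. At H8 the stopped patients come back, with a value that may have been taken hours earlier at the moment of stopping. At H9 to H11.5 their values are off-drug readings from a different clock time than those of their neighbours in the same row.

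Hypotension is the immediate effect the protocol expects from excess drug (Protocol 8.3). Apart from hypotension reported as an adverse event, Table 14.3.6 is the only planned between-treatment summary of blood pressure. A reader who takes it as the course of SBP on drug could see an apparent recovery before H8 and a drop at H8, both produced by how the rows are filled.

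**Working it through.** The documents give no figure for missing vital signs or for the size of the SBP change, so there is none to reproduce.

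**Step 1: which labels are lost.** Inputs: readings at 0.5 h, 1 h and then hourly until discontinuation (SAP Appendix 2), and the re-timing in Protocol 1.3, Table 2, footnote a. For a stop at time t, the labels H8, H9, H10 and H11.5 fall at t, t + 1, t + 2 and t + 3.5 hours.

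| Stop (h) | Hourly labels with no value | Clock time of H8 / H9 / H10 / H11.5 (h) |
|---|---|---|
| 2.5 | H3 to H7 | 2.5 / 3.5 / 4.5 / 6.0 |
| 4.5 | H5 to H7 | 4.5 / 5.5 / 6.5 / 8.0 |
| 5.5 | H6, H7 | 5.5 / 6.5 / 7.5 / 9.0 |
| 6.5 | H7 | 6.5 / 7.5 / 8.5 / 10.0 |
| 7.5 | none | 7.5 / 8.5 / 9.5 / 11.0 |

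**Step 2: direction and possible size at a lost label.** Let n = 20 infusions, k stopped, c the mean change in continuing patients and s the change in stopped patients. The table shows c. The mean over everyone is [(n − k)c + ks]/n. The difference is (k/n)(c − s); a positive value means the fall is understated.

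k and c are assumed. Values of s come from the protocol's limits, starting at the lowest permitted pre-dose SBP of 115 mmHg (Protocol 5.2, applied on each treatment day by 4.1): SBP below 80 is a fall of more than 35, entered as −36; SBP below 105 is a fall of more than 10, entered as −11; full recovery is 0. A higher starting pressure makes the first two falls larger.

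With c = −15 mmHg:

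| s (mmHg) | k = 2 | k = 4 | k = 6 |
|---|---|---|---|
| −36 | +2.1 | +4.2 | +6.3 |
| −11 | −0.4 | −0.8 | −1.2 |
| 0 | −1.5 | −3.0 | −4.5 |

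For example, k = 4 and s = −36 gives 0.2 × (−15 + 36) = +4.2. With c from −10 to −20 and k from 1 to 6, the range is from 0.3 × (−10 + 36) = +7.8 to 0.3 × (−20 − 0) = −6.0. The sign depends on whether the missing value is the pressure the patient would have had on drug or the pressure actually present after stopping.

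**Step 3: the step at H8.** Keep c = −15 and k = 4. The H7 mean is −15.0, from 16 patients. If the four re-timed H8 readings are −36, the H8 mean is (16 × −15 + 4 × −36)/20 = −19.2, a drop of 4.2 mmHg with no change in any continuing patient. If they are −11, it is (−240 − 44)/20 = −14.2.

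**Step 4: simulation with the hourly schedule.** All inputs are assumed: baseline about 130 mmHg truncated at 115; within-patient SD 7 to 8; stop at SBP below 80 or at a second reading below 90; no restart; no effect of dose reduction. The ranges cover runs with slightly different assumed spreads.

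| Mean fall (between-patient SD) | Stopped by H7 | H7 mean shown | H8 mean with stop readings included |
|---|---|---|---|
| 15 (10) | 6–8% | −13.8 to −14.0 | −15.0 to −15.9 |
| 20 (12) | 14–19% | −16.9 to −17.5 | −20.0 to −21.6 |

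Against the on-drug fall, H7 is understated by 1.0 to 1.2 mmHg in the first case and 2.5 to 3.1 in the second. If stopped patients instead recover over 1.5 hours (also assumed), the actual mean change at H7 in all patients is about −13 and −15, against about −14 and −17.5 in those still observed. The table then overstates the fall.

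**The case against.** A reader might infer that scheduled blood pressure ends with the infusion, so that patients stopped for hypotension vanish and the late fall is understated throughout. The documents do not support that. The same schedule row continues at H9, H10 and H11.5, footnote a keeps H8 to H11.5 for every early stop, and Protocol 7.1 holds stopped patients to the schedule. The loss is confined to the hourly labels between the stop and H7, and at H8 the distortion can run the other way.

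The direction before H8 also depends on the target. The fall a stopped patient would have had on continued drug is hypothetical, and Protocol 8.3 reports that pressure was restored within 1 to 2 hours of stopping in previous studies. Against actual pressure at that clock hour, the sign can reverse.

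The simulation simplifies Protocol 6.4, which allows interruption and resumption at half dose; leaving out any benefit of dose reduction probably inflates the number stopped. Protocol 6.4 also lists SBP below 80 or symptoms under both interruption and permanent discontinuation, and those passages must be reconciled before anyone could predict how often infusions stop. The modelled biases are no larger than about one standard error with 20 patients: √(10² + 8²)/√20 = 2.9 and √(12² + 8²)/√20 = 3.2 mmHg.

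Other outputs help. Summaries report n (SAP 8.1.3), full-dose receipt is tabulated (SAP 14.0), discontinuations due to adverse events are counted by treatment (SAP 16.2.1), and all vital signs are listed.

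These points limit the claim but do not remove it. A falling n does not tell the reader that the loss is driven by SBP. A systematic shift is not excused by being of the order of a standard error. None of the listed outputs summarises each patient's on-infusion pressure by treatment.

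**Conclusion.** The point holds in a limited form and calls for a low-cost improvement. The by-time table drops patients stopped for low SBP at the labels between the stop and H7, for a reason tied to the outcome. From H8 onward it mixes nominal-time readings with readings re-timed to the stop. Before H8 the BMS-986231 means can understate the on-infusion fall; at H8 the mean can be pulled down; neither is certain.

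The documents cannot fix the size. About 1 to 3 mmHg at H7 rests entirely on the assumed falls, spreads and simplified stopping rule of Step 4, and on taking the effect while on drug as the target. The claim that the late fall is understated throughout is not established. Nor is any inferential conclusion at risk, since the table is descriptive.

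**What to change.** In SAP 16.2.4, derive for each patient and period:

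- the lowest SBP during infusion, using all readings, including unscheduled ones and the reading that led to the stop;
- the change from baseline to the last on-infusion SBP.

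Summarise both by treatment, with the paired BMS-986231 minus placebo difference and its 95% CI, and base the statement on blood pressure during infusion on these. Every stopped patient is kept, and neither measure depends on hourly or re-timed labels. A patient with only one infusion enters the summary but not the paired difference.

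In the by-time table, show how many infusions had already stopped at each time, and present re-timed post-stop readings separately from nominal-time readings. Restricting late time points to patients observed in both periods would not help: it keeps the same selected BMS-986231 patients and removes only their counterparts' placebo values.

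The cost is SAP wording, two derived variables and one table, with no new data and no change to how patients are managed. There are two small drawbacks: the lowest value is pulled down by extra readings taken after a low one, and the last on-infusion value mixes infusion durations. Reporting both lets each be read against the other.
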